3.2 Exclusion Criteria

Create a numbered list of the exclusion criteria that define who will be excluded in your study.

1. Infants who weigh less than their birthweight 21 days after delivery

3.3 Early Withdrawal of Subjects

3.3.1 Criteria for removal from study

Insert subject withdrawal criteria (e.g., safety reasons, failure of subject to adhere to protocol requirements, subject consent withdrawal, disease progression, etc.).

1. Infants exhibiting failure-to-thrive defined as:
 - a. Weight-for-length $< 5^{\text{th}}$ percentile for sex and age on the WHO growth chart
 - b. Downward crossing of > 2 major centile lines on the WHO growth chart (relevant major lines include 95th, 90th, 75th, 50th, 25th, 10th, 5th) after enrollment
2. Non-adherence to the study visit schedule characterized by failing to complete **two** scheduled study intervention visits within 2 weeks of turning 1, 2, 3, 4, and 5 months old (does not include enrollment and final visit)

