1.3 Secondary Study Endpoints

State the secondary endpoints to be measured in the study.

- Conditional Weight Gain during the intervention period spanning Ages 1-6 Months
- Mean Weight-for-Length Z-score (WLZ) at Age 6 Months
- Growth Trajectory during the intervention period spanning Ages 1-6 Months (repeated measures of weight-for-length)
- Proportion of Infants with Overweight (Weight-for-Length $\geq 95^{\text{th}}$ Percentile on WHO Growth Charts) at Age 6 months
- Feasibility: a) recruitment, b) ability to give tailored formula volume recommendations, c) visit completion, d) retention through 6 months
- Acceptability: parent adherence to formula volume recommendations as measured by 3 day feeding diaries at 2, 3, 4, 5, and 6 months for the intervention group

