3.3.2 Follow-up for withdrawn subjects

Describe when and how to withdraw subjects from the study; the type and timing of the data to be collected for withdrawal of subjects; whether and how subjects are to be replaced; the follow-up for subjects withdrawn from investigational treatment.

Study personnel will contact consenting parents by phone notifying them of their removal from the study and the reason for withdrawal. If the reason is due to failure-to-thrive, the infant's pediatrician will also be notified. If study personnel are unable to reach the consenting parent, a letter will be sent via US mail.

No further data will be collected on participants that are withdrawn, and these participants will not be replaced.

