7.1 Study Design

Describe and explain the study design.

This study is a randomized, clinical trial involving 60 exclusively formula fed infants born at ≥ 37 weeks gestational age who are at-risk for overweight based upon maternal pre-pregnancy overweight or obesity (or alternatively at first prenatal visit if pre-pregnancy weight/height not known) and infant birthweight $\geq 50^{\text{th}}$ percentile. Infants will be enrolled at Penn State Health Children's Hospital or at affiliated clinics within the Division of Academic General Pediatrics between birth and age 1 month, where they will be randomized to a calibrated formula intake intervention or control. Participating infants in the intervention group will be seen monthly until age 6 months where they will be weighed and measured, and parents will complete surveys related to volume of formula consumed, infant appetite, parent feeding style, and infant temperament. Control infants will follow the same procedures, but will not have scheduled visits at ages 3 and 5 months. Instead their visits will correspond to usual care well child visits at ages 1, 2, 4, and 6 months.

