Age (months)	Weight (kg) ^a	Weight velocity (g day ⁻¹) ^b	Total energy expenditure (kJ day ⁻¹)	Total energy expenditure (kcal day ⁻¹)	Energy deposition (kJ day ⁻¹)	Energy deposition (kcal day ⁻¹)	Energy requirement (kJ day ⁻¹)	Energy requirement (kcal day ⁻¹)	Energy requirement (kJ kg ⁻¹ per day)	Energy requirement (kcal kg ⁻¹ per day)
Boys										
1	4.58	35.2	1462	349	884	211	2345	560	512	122
2	5.5	30.4	1779	425	764	183	2543	608	462	111
3	6.28	23.2	2049	490	582	139	2631	629	419	100
4	6.94	19.1	2277	544	224	53	2501	598	360	86
5	7.48	16.1	2464	589	189	45	2653	634	355	85
6	7.93	12.8	2619	626	150	36	2770	662	349	83
7	8.3	11.0	2747	657	69	17	2816	673	339	81
8	8.62	10.4	2858	683	65	16	2923	699	339	81
9	8.89	9.0	2951	705	57	14	3008	719	338	81
10	9.13	7.9	3034	725	89	21	3123	746	342	82
11	9.37	7.7	3117	745	87	21	3204	766	342	82
12	9.62	8.2	3203	766	93	22	3296	788	343	82
Girls										
1	4.35	28.3	1382	330	746	178	2128	509	489	117
2	5.14	25.5	1655	396	672	161	2327	556	453	108
3	5.82	21.2	1890	452	559	134	2449	585	421	101
4	6.41	18.4	2094	500	285	68	2379	569	371	89
5	6.92	15.5	2270	543	239	57	2510	600	363	87
6	7.35	12.8	2419	578	199	47	2617	626	356	85
7	7.71	11.0	2543	608	83	20	2626	628	341	81
8	8.03	9.2	2654	634	69	17	2723	651	339	81
9	8.31	8.4	2751	657	63	15	2814	673	339	81
10	8.55	7.7	2834	677	74	18	2908	695	340	81
11	8.78	6.6	2913	696	63	15	2976	711	339	81
12	9	6.3	2989	714	60	14	3049	729	339	81

^a50th percentile weight for age of the WHO pooled breast-fed data set³⁶.

^b50th percentile weight increment of the WHO pooled breast-fed data set³⁶.

Recommended formula volumes will be calculated based on data from the table above informing parents of the recommended formula volume based on 19/20 kcal/ounce formula at the infant’s current age as well as the anticipated volume at the infant’s next visit as described below.

For those with weight-for-length (WFL) <75th percentile on the WHO WFL growth chart, recommended daily formula volumes will be calculated based upon the infant’s sex, current age, weight, and energy requirement (kcal/kg/day). Further, parents will be informed of the volume to expect at the subsequent visit in one month should the child maintain the same weight-for-age percentile.

For those with WFL ≥75th percentile on the WHO WFL growth chart, recommended daily formula volumes will be calculated based upon the child’s current age, weight, and energy requirement (kcal/kg/day) with a 10% reduction in daily volume. Further, parents will be

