8.2 Sample size determination

If applicable, provide a justification of the sample size outlined in section 8.1 to include reflections on, or calculations of, the power of the study.

The sample size for this pilot study is based upon the number of participants that we felt we could feasibly recruit given the time and resources available for recruitment. As this pilot is going to determine feasibility, 60 participants should be adequate. Further, we will use the data generated to determine the sample size necessary for a fully powered subsequent trial.

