8.3 Statistical methods

Describe the statistical methods (or non-statistical methods of analysis) that will be employed.

We will assess conditional weight gain from birth to 6 months to assess rapid infant growth.^{80,81} Conditional weight gain will be calculated as standardized residuals from the linear regression of weight for age at 6 months on weight for age at birth, with length for age at birth and 6 months and infant age at the 6-month visit entered as covariates. We will explore the moderating role of child sex, delivery mode, and maternal parity on intervention effects. Similar analyses will be conducted for the intervention period spanning ages 1-6 months.

For cross-sectional analyses at age 6 months, ANOVA will estimate the effects of intervention group on mean weight-for-length. Logistic regression will be used to compare intervention effects on the dichotomous outcome of overweight at 6 months.

For growth from 1-6 months, we will fit a repeated measures ANOVA of BMI, with visit and study group as within and between factors, respectively.

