10.0 Risks

List the reasonably foreseeable risks, discomforts, hazards, or inconveniences to the subjects related to the subjects' participation in the research. Include as may be useful for the IRB's consideration, a description of the probability, magnitude, duration and reversibility of the risks. Consider all types of risk including physical, psychological, social, legal, and economic risks. Note: Loss of confidentiality is a potential risk when conducting human subject research.

- If applicable, indicate which procedures may have risks to the subjects that are currently unforeseeable.
- If applicable, indicate which procedures may have risks to an embryo or fetus should the subject be or become pregnant.
- If applicable, describe risks to others who are not subjects.

It is possible that a reduction in formula intake could lead to temporary growth faltering (i.e. failure-to-thrive), though this would be self-limited and could be addressed by subsequently increasing formula intake.

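### Withdrawal under Section 3.3.1 ends all measurement, so an infant removed before Visit 7 has no 6-month primary endpoint, and recovery from growth faltering is never observed

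*Combined protocol and SAP*

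**What the plan says.** Section 3.3.1 gives two grounds for removal. Ground 1 is failure-to-thrive, with two sub-items: (a) weight-for-length under the 5th percentile, and (b) "Downward crossing of > 2 major centile lines on the WHO growth chart (relevant major lines include 95th, 90th, 75th, 50th, 25th, 10th, 5th", counted after enrollment. The text does not say whether (a) and (b) are alternatives, or which chart (b) uses. Ground 2 is failing to complete two of the scheduled visits at 1 to 5 months.

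Section 3.3.2 applies to both grounds: "No further data will be collected on participants that are withdrawn". Removed infants are not replaced. After a failure-to-thrive removal the pediatrician is told.

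Section 8.3 defines the primary endpoint as "standardized residuals from the linear regression of weight for age at 6 months on weight for age at birth", with length and visit age as covariates. It gives no analysis population and no missing-data method.

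Section 9.1 has growth charts reviewed at each visit. Section 7.1 has the intervention arm seen monthly, while controls "will not have scheduled visits at ages 3 and 5 months". Section 10.0 lists growth faltering as the risk and says "this would be self-limited and could be addressed by subsequently increasing formula intake". Section 1.3 makes "d) retention through 6 months" a feasibility endpoint.

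**The concern.** Stopping the study feeding advice and stopping measurement are separate decisions, and Section 3.3.2 makes them one. Three things are at stake.

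- **Primary endpoint.** An infant removed before Visit 7 has no 6-month weight. When the removal is for falling growth, the missing values belong to the infants whose weight fell most. Losing more of them from the arm meant to slow weight gain would shrink the observed effect.
- **Safety information.** The plan regards faltering as temporary and correctable, but study observation ends when faltering is found. Neither recovery nor persistence can enter the data. This holds for (a) as well as (b), and for any degree of growth tracking.
- **Feasibility.** Removals made by rule count against retention unless they are reported apart from parents' decisions to leave. With 30 per arm (assumed; no allocation ratio is stated), each removal costs 1/30 = 3.3 percentage points of that arm's retention.

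**Working it through.** The plan has no power calculation or expected removal rate to reproduce; Section 8.2 rests the size of 60 on feasibility. The check therefore has a part that follows from the text and a part that needs assumptions.

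**1. What rule (b) can catch.** More than two lines means at least three. The listed lines lie at z = 1.645, 1.282, 0.674, 0, -0.674, -1.282 and -1.645. The smallest three-line falls are:

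| From | To below | Fall in z |
|---|---|---|
| 95th | 75th | 1.645 - 0.674 = 0.97 |
| 90th | 50th | 1.282 - 0 = 1.28 |
| 75th | 25th | 0.674 + 0.674 = 1.35 |
| 50th | 10th | 0 + 1.282 = 1.28 |
| 25th | 5th | -0.674 + 1.645 = 0.97 |

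Four of the five can end above the 5th percentile. If (a) and (b) are alternatives, which is the natural but unstated reading, (b) can therefore remove an infant in the normal range. Read on weight-for-length, the first row ends where Section 7.2.2 already drops the volume reduction ("For those with weight-for-length (WFL) <75th percentile on the WHO WFL growth chart"), so the plan's own correction would go unobserved.

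**2. When the endpoint is lost.** A crossing first seen at Visit 7 loses nothing, because the 6-month weight exists. Before that, the intervention arm is checked at months 1, 2, 3, 4 and 5 (five checks), and controls at 1, 2 and 4 (three).

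**3. Possible size.** The documents give no growth correlations, so every input here is an assumption:
- 30 infants per arm; normal z with SD 1 and enrollment mean 0 or 0.5;
- control drift of 0 or +0.3 z by month 6; true effect of -0.3 or -0.5 z, building linearly;
- correlation between months s and t equal to r^(|s-t|/6);
- lost = meets (b) but not (a), on one z-score, before month 6;
- endpoint = standardized residual of 6-month z on enrollment z, as a stand-in for the Section 8.3 regression.

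Bias is the completers' group difference minus the full-data difference.

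| r, enrollment to 6 months | Lost of 30, intervention | Lost of 30, control | Completers / full | Bias (SD) |
|---|---|---|---|---|
| 0.4 to 0.8 | 0.2-4.7 | 0.03-1.8 | 79-99% | 0.01-0.08 |
| 0.6 | 1.1-2.9 | 0.3-0.7 | 87-94% | 0.03-0.06 |
| 0.9 | 0.01-0.2 | about 0 | above 99% | below 0.01 |

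For comparison, the standard error of a difference in a standardized outcome is sqrt(1/30 + 1/30) = sqrt(2/30) = 0.26 SD. The largest bias in the table is 0.08/0.26 = 0.3 standard errors.

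**4. Sensitivity to the assumptions.**
- *All infants start at or above the 50th percentile, all (b) crossings count, monthly correlation 0.90, 0.94 or 0.97.* At 0.94 (0.94^6 = 0.69 over six months) and an effect of -0.3 z, removal is 7.5% against 2.1%. The difference is -0.406 SD in full data and -0.343 in completers, a bias of 0.063. With effects of -0.3 and -0.5 z, the bias runs from 0.523 - 0.505 = 0.02 (correlation 0.97) to 0.563 - 0.434 = 0.13 (correlation 0.90).
- *Same model, no true effect.* Removal is 10.5% against 6.1%, 4.1% against 2.1%, and 0.6% against 0.3% at monthly correlations 0.90, 0.94 and 0.97. This gap comes from the two extra visits alone.
- *Equal correlation 0.4-0.8 between all visits, other inputs as in step 3.* 0.8-8.1 against 0.4-4.7 of 30; completers/full 90-98%.
- *(b) read on weight-for-age, starts at or above the 50th percentile.* 0.3-8.6 against 0.05-3.2 of 30; completers/full 57-98%.

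The direction is the same throughout. The size depends almost wholly on the assumed tracking.

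**The case against.** **The removal threshold is a precaution.** In a trial that lowers infants' intake, where to set (b) is a clinical judgement. A reader might infer from step 1 that (b) is wrong and needs a floor percentile. The documents do not support that. The normal-range case depends on the unstated either/or reading, and the data loss comes from Section 3.3.2 whatever (b) says. This objection stands, and the fix leaves (b) alone.

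**The arm imbalance is inferred.** No document gives a removal rate. A reader might conclude that losses fall mainly on the intervention arm. At the upper ends of the equal-correlation runs, controls make up 4.7/(8.1 + 4.7) = 37% of removals, so that is too strong. Likely to be more frequent is as far as the visit schedule and the aim of the intervention carry.

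**The bias is small and modelled generously.** One z-score serves as both flag and endpoint, whereas Section 8.3 uses weight-for-age adjusted for length. With an assumed flag-endpoint correlation of 0.6 to 0.8, the largest bias in the step 3 runs falls from 0.08 to about 0.05-0.07 SD. This stands.

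**The next trial's size.** Section 8.2 says "we will use the data generated to determine the sample size necessary for a fully powered subsequent trial". A reader might infer that the next trial will be oversized by a calculable factor. That sentence does not say the effect estimate will be used; it could mean the SD or retention. Even if the estimate is used, chance dominates. At a true difference of 0.4 SD, a one-standard-error miss multiplies the implied size by (0.40/0.66)^2 = 0.37 or (0.40/0.14)^2 = 8.2.

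**Safety is partly covered.** Growth failure is flagged at once (Section 9.1), recorded as an adverse event (9.3) and reported to the pediatrician (3.3.2), and usual care continues (15.4). Recovery is lost to the dataset, not to the child's care. The reason for removal must be given to the parent, so rule-based removals could already be told apart from dropout. What remains is that Section 3.3.2 bars the study from collecting weights that routine care will probably produce.

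**Conclusion.** The point holds for Section 3.3.2. Following the plan as written, any infant removed under 3.3.1 before Visit 7 leaves the primary analysis. For failure-to-thrive removals that loss depends on the outcome, and the course of the one listed risk is not observed. These conclusions come from the text and do not depend on how (a) and (b) combine or which chart (b) uses. Non-adherence removals lose the endpoint in the same way.

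The numerical effect rests on assumptions. The step 3 runs give a pull toward zero of about 0.01-0.08 SD. Starting every infant at or above the 50th percentile with loose tracking raises this to 0.13 SD, half of the 0.26 SD standard error. With tight tracking it is negligible. The documents do not support a claim that the pilot's result would be materially distorted. The case for change is that the lost data bear on the primary endpoint and the main safety question, and cost very little to keep.

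**What to change.** Leave the 3.3.1 triggers, the immediate review, the pediatrician notice and the end of volume advice unchanged. Then:

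1. In Section 3.3.2, state that for any infant removed under 3.3.1(1) or 3.3.1(2), unless the parent withdraws consent, weight and length are still recorded at the 6-month well-child visit, and at 2 and 4 months if those are still to come.
2. In Section 8.3, analyse these infants in their randomized arm for the primary endpoint, with completers-only as a sensitivity analysis.
3. In the retention endpoint, report rule-based removals separately from parental dropout.

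The cost is a sentence in the consent form and about 15 minutes (the figure in Section 7.3) at a visit that families already intend to make at the same practices (Section 3.1). Some parents may decline. The 6-month value of a removed infant will reflect assignment to the feeding strategy, not full adherence to it, and the report should say so.

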1.2 Primary Study Endpoints

State the primary endpoints to be measured in the study.

Clinical trials typically have a primary objective or endpoint. Additional objectives and endpoints are secondary. The endpoints (or outcomes), determined for each study subject, are the quantitative measurements required by the objectives. Measuring the selected endpoints is the goal of a trial (examples: response rate and survival).

- Conditional Weight Gain between Birth and Age 6 months

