informed of the volume to expect at the subsequent visit in one month should the child maintain the same weight-for-age percentile, again with a 10% reduction.

10% was chosen for this pilot because it balances feasibility (relatively likely that parents can comply) and safety (unlikely to cause failure-to-thrive by reducing total daily formula volume by ~3 ounces)

6. Parents will be given instruction to prepare the formula volume in each bottle on the lower end of what they anticipate the infant will eat. For example, if they anticipate the infant will consume 3-4 ounces per feed, they will prepare 3 ounces at first. If hunger cues persist, they will then prepare an additional 1-2 ounces of formula.

7.2.3 Visit 3

Age 2 Month Visit (42-77 days)

Both study groups:

1. Anthropometrics of infant (weight, recumbent length)
2. Diary cards to be completed for the 3 days following the visit
3. Diary cards to be completed x 3 days prior to next study visit

Intervention group only:

1. Recommend formula volumes for the next month based on Visit 2 procedures
2. **If, for a second consecutive month, the child has WFL \geq 75th percentile on the WHO WFL growth chart**, recommended daily formula volumes will be calculated based upon the child's current age, weight, and energy requirement (kcal/kg/day) with a 15% reduction in daily volume. Further, parents will be informed of the volume to expect at the subsequent visit in one month should the child maintain the same weight-for-age percentile, again with a 15% reduction.

7.2.4 Visit 4

Age 3 Month Visit (78-109 days): Intervention group only

1. Anthropometrics of infant (weight, recumbent length)
2. Diary cards to be completed for the 3 days following the visit
3. Diary cards to be completed x 3 days prior to next study visit
4. Recommend formula volumes for the next month based on Visit 2 and 3 procedures

7.2.5 Visit 5

Age 4 Month Visit (110-140 days)

Both study groups:

1. Anthropometrics of infant (weight, recumbent length)
2. Diary cards to be completed for the 3 days following the visit
3. Diary cards to be completed x 3 days prior to next study visit

Intervention group only:

4. Recommend formula volumes for the next month based on Visit 2 and 3 procedures

5. Provide handouts on soothing fussy infants, feeding

7.2.6 Visit 6

Age 5 Month Visit (141-171 days) – Intervention Group Only

1. Anthropometrics of infant (weight, recumbent length)

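### The missed-visit removal rule discards the 6-month weight and exposes the intervention arm to five countable visits against three for control

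*Combined protocol and SAP*

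**What the plan says.** Section 3.3.1 (item 2) removes an infant for failing to complete two "scheduled study intervention visits within 2 weeks of turning 1, 2, 3, 4, and 5 months old". The enrollment and final visits do not count. Section 3.3.2 adds: "No further data will be collected on participants that are withdrawn". Such infants are not replaced.

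The two arms have different schedules. Intervention infants are seen monthly to 6 months. Section 7.1 says of the others: "Control infants will follow the same procedures, but will not have scheduled visits at ages 3 and 5 months". It continues: "Instead their visits will correspond to usual care well child visits at ages 1, 2, 4, and 6 months". Section 7.2 likewise marks the 3- and 5-month visits as being for the intervention group only.

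Section 7.2 also sets its own visit windows: days 24–41, 42–77, 78–109, 110–140 and 141–171 for months 1 to 5.

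The primary endpoint in Section 1.2 is "Conditional Weight Gain between Birth and Age 6 months". Section 8.3 computes it as "standardized residuals from the linear regression of weight for age at 6 months on weight for age at birth", with length and age covariates. Section 8.3 names no analysis population and no method for missing outcomes.

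**The concern.** Removal under this rule must happen before the 6-month visit, so every infant it removes is an infant without a primary outcome. Whether a family misses visits reflects how engaged the parents are, and engagement may well be related to feeding and growth. Outcomes lost this way are unlikely to be lost at random.

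The rule also treats the arms differently by construction. The intervention arm has five opportunities to accumulate two failures and control has three. The infants left at 6 months may then be selected more heavily in one arm, and the comparison is no longer between the groups as randomised.

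There is a second fault in the same rule. Its 2-week limit does not match the Section 7.2 windows, so a visit can be on time for the schedule and still count as failed for removal.

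**Working it through.** **Inputs from the documents.** Countable visits: intervention 1, 2, 3, 4, 5 (n = 5); control 1, 2, 4 (n = 3) (Sections 3.3.1, 7.1, 7.2). Removal at two failures. Total sample 60 (Section 8.1). The plan states no retention or dropout figure, so there is none to reproduce.

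**Assumptions.** A per-visit miss rate p that is equal in both arms; a within-family correlation ρ; 30 infants per arm (the allocation ratio is not stated).

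**Direction.** Control's three visits are a subset of the intervention arm's five. At a common miss rate, the chance of at least two misses cannot be lower in the intervention arm. It is strictly higher unless misses within a family coincide perfectly.

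**Size, independent misses.** P(X ≥ 2) = 1 − (1 − p)^n − n·p·(1 − p)^(n−1).

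- p = 0.10, n = 5: 1 − 0.5905 − 0.3281 = 0.081. n = 3: 1 − 0.729 − 0.243 = 0.028.
- p = 0.20, n = 5: 1 − 0.3277 − 0.4096 = 0.263. n = 3: 1 − 0.512 − 0.384 = 0.104.

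**Size, correlated misses.** Beta-binomial with a = p(1/ρ − 1) and b = (1 − p)(1/ρ − 1). For p = 0.20 and ρ = 0.5, a = 0.2 and b = 0.8:

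- n = 5: P(0) = (0.8·1.8·2.8·3.8·4.8)/120 = 0.613; P(1) = 5·0.2·(0.8·1.8·2.8·3.8)/120 = 0.128; P(X ≥ 2) = 0.259.
- n = 3: P(0) = (0.8·1.8·2.8)/6 = 0.672; P(1) = 3·0.2·(0.8·1.8)/6 = 0.144; P(X ≥ 2) = 0.184.

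| p | ρ | Intervention | Control | Ratio | Expected removals per 30 | Excess |
|---|---|---|---|---|---|---|
| 0.10 | 0 | 8.1% | 2.8% | 2.9 | 2.4 vs 0.8 | 1.6 |
| 0.10 | 0.3 | 13.1% | 7.3% | 1.8 | 3.9 vs 2.2 | 1.7 |
| 0.10 | 0.5 | 13.0% | 8.8% | 1.5 | 3.9 vs 2.6 | 1.3 |
| 0.20 | 0 | 26.3% | 10.4% | 2.5 | 7.9 vs 3.1 | 4.8 |
| 0.20 | 0.5 | 25.9% | 18.4% | 1.4 | 7.8 vs 5.5 | 2.3 |

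**Existing safeguard.** Section 9.8 suspends the study if attrition exceeds 33% after Visit 2, with no split by arm. At p = 0.20 with independent misses, overall removal is (26.3 + 10.4)/2 = 18.4%. The trigger would stay silent despite a 16-point gap between arms.

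**Window conflict.** With a 30.44-day month, the 2-week limit compares with the Section 7.2 windows as follows.

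| Month | Section 7.2 window | ±14 days | In-window days outside the limit |
|---|---|---|---|
| 1 | 24–41 | 16.4–44.4 | none |
| 2 | 42–77 | 46.9–74.9 | 8 of 36 |
| 3 | 78–109 | 77.3–105.3 | 4 of 32 |
| 4 | 110–140 | 107.8–135.8 | 5 of 31 |
| 5 | 141–171 | 138.2–166.2 | 5 of 31 |

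These are shares of days, not removal probabilities, since removal needs two failures. The conflict does not depend on the average month length. By calendar date, 2 months falls at most 62 days after birth and 4 months at most 123 days. Visits on day 77 (77 − 62 = 15) and day 138 (138 − 123 = 15) are therefore always more than 14 days late, although both are inside their windows. That infant has attended on schedule and still meets the removal rule.

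**The case against.** The strongest reply is that the size is unknown. The documents give no miss rate, no correlation and no allocation ratio, and equal miss rates are themselves an assumption. Intervention families have more contact, extra materials and up to $300 against $250 (Section 13.0), so they might attend better. With independent misses, 10% in the intervention arm against 18% in control gives 8.1% versus 8.6%, and the imbalance disappears. This stands as a limit on the magnitude. It can also go the other way, because the 3- and 5-month visits lie outside usual well-child care and may be missed more often.

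Second, families who miss two visits may be the ones who would miss the 6-month visit anyway, so the table counts removals and not outcomes lost solely because of the rule. This is fair, and the excess counts are upper-end figures for lost outcomes. But eligibility requires intended well-child care at the study practices through 6 months (Section 3.1, item 8), and Section 13.0 pays $150 at Visit 7. Some of these weights should be obtainable, and the protocol rules out collecting them.

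Third, the rule's wording could mean intervention-arm visits only. Controls would then have no countable visits and the asymmetry would be larger.

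Fourth, the day 77 and day 138 example uses visits that both arms attend and lies near the late edge of both windows. It shows an inconsistent rule, not unequal loss, and is the lesser part of the point.

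Finally, this is a feasibility-sized pilot. Its primary endpoint is nonetheless a 6-month weight outcome, and Section 8.2 says its data will size the next trial.

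**Conclusion.** The concern holds. Three things follow from the text alone: five countable visits against three, no data after removal, and a 2-week limit that contradicts the Section 7.2 windows at months 2 to 5. Nothing elsewhere in the document restores the 6-month weight.

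The size is illustrative. With equal miss rates and 30 per arm, the intervention arm would have about 1 to 2 more infants removed at a 10% miss rate and 2 to 5 more at 20%, over the correlations examined. The direction is assured only if miss rates are equal across arms. The rule should be changed because the loss is avoidable, can differ by arm and affects the primary outcome directly.

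**What to change.** In Section 3.3.2, for infants removed for visit non-adherence, continue to collect weight and length at the 6-month well-child visit unless the parent withdraws consent. In Section 8.3, state that all randomised infants are analysed in their assigned arm. In Section 3.3.1, define a completed visit as one falling inside its Section 7.2 window, so that a single definition governs both schedule and removal.

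The first change means the rule itself no longer causes loss of primary-endpoint data in either arm. It leaves five against three countable visits for the retention endpoint. If that comparison matters, the rule could count only the shared visits at 1, 2 and 4 months. With independent misses at equal rates, removal would then be the same in both arms (2.8% at a 10% miss rate, 10.4% at 20%).

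The cost is protocol wording and some effort to follow non-adherent families. The 6-month visit is usual care, so the two measurements add little.
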